Given the fact that we are going to provide to healthy people a drug that has not been used before for this indication and which has only been conditionally approved for use in multi-drug resistant tuberculosis, we have first foreseen a phase 2 study in which BE-PEP will be provided to a limited number of contacts and in which safety will be closely monitored and evaluated by an independent data and safety monitoring board (DSMB). This will be done in a small village that is part arm 1 of the PEOPLE trial in which 8 new cases have been diagnosed since 2019 but no PEP has been provided. We will conduct door-to-door screening in this village in June 2022 and offer a single dose of BE-PEP to a random sample of 150 people screened aged 5 years and above not meeting the exclusion criteria (active TB or leprosy or previously treated leprosy, known liver function or cardiac abnormalities, not able to swallow 100 mg bedaquiline tablets). Participants will be followed up closely with active monitoring for adverse events, including measurement of the corrected QT interval and liver function before and after administration, as well as gastro-intestinal (nausea, vomiting), nervous system-related (headache, dizziness) and cutaneous reactions. The remainder of the population of this village aged two years and above will be offered single dose rifampicin as per WHO recommendations. In a randomly sampled subset of 150 individuals receiving rifampicin only we will perform the same stringent monitoring with ECG and liver function tests also applied in those receiving BE-PEP.

Assuming the phase 2 study will not reveal any drug related adverse events and following the advice of the DSMB and the involved ethics committees, we will proceed with a phase 3 study for which randomization will take place in early2023. There will be two study arms. Arm 1 will be the intervention arm in which we will provide BE-PEP to all persons residing within 100 meters of an index case, to be repeated after four weeks for household contacts. Arm 2 will be the comparator arm in which the WHO recommended standard PEP will be provided, i.e. 10 mg/kg of rifampicin in a single dose. PEP distribution and eligibility will be evaluated at village level once the annual screening round in the

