3. STUDY DESIGN

3.1 General study design

We will conduct a phase 3 intervention trial comparing the effectiveness of two different regimens of post exposure prophylaxis for leprosy. Because we will be using a new drug (bedaquiline) that has not been used before for this indication, we have planned a phase 2 safety study to start in July, 2022. For this study we will select a small village (Gégé, Anjouan) that is part of the comparator arm of the PEOPLE trial and in which to date eight leprosy cases were diagnosed but that will not be included in the BE-PEOPLE trial because of its small population size (n=908). In this village, in May 2022, we will conduct the final round of door-to-door screening for leprosy in the framework of the PEOPLE trial. All cases identified will be treated in accordance with the national standards. Upon completion of screening, a random sample of 150 participants not meeting the exclusion criteria will be offered BE-PEP with strict monitoring for adverse events, in particular ECG and liver function will be monitored pre- and post-drug administration. The remainder will receive single dose rifampicin (SDR-PEP), as per WHO recommendation. Of those a random sample of 150 will also be subjected to the same procedures for monitoring adverse events as those receiving BE-PEP. Results will be presented to an independent data safety management board and the regulatory authority in the Comoros who will then decide whether or not the main phase 3 trial can go ahead. The full BE-PEOPLE study is expected to run from January, 2022 until 4 year follow-up is finished in all phase 3 participating villages (expected by the start 2027) A Gantt chart of the main project activities is presented in figure 2 below.

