4.2 Study population and selection criteria

For the phase 2 study we have selected the village of Gégé, a leprosy endemic village on the island of Anjouan at one hours' driving distance of the main hospital in the capital. The village has an estimated population of approximately 900 and is currently part of arm 1 of PEOPLE, the comparator arm. Therefore no PEP has been provided yet although 8 leprosy cases were diagnosed during the PEOPLE trial so far. The village will be screened once more in the framework of the PEOPLE trial, in May, 2022. After this final screening, BE-PEP and SDR-PEP will be provided for the phase 2 study of BE-PEOPLE. The village will not be part of the phase 3 study of BE-PEOPLE. A random sample of 150 eligible participants will receive BE-PEP, the remainder will receive SDR-PEP. Those receiving BE-PEP as well as a random sample of 150 among those receiving only SDR-PEP will be strictly monitored for adverse events. As an additional safety measure BE-PEP administration will start with adults 18 years and older, followed by children aged 13-17, and finally children aged 5-12. Provision of BE-PEP to children aged 13-17 will start once post BE-PEP QTc measurements for adults are available and have shown no indication for concern, similarly distribution to children aged 5-12 will start once post BE-PEP QTc measurements for children aged 13-17 are available and show no reasons for concern.

Inclusion and exclusion criteria for the phase 2 study will be the following:

Inclusion criteria:

1. Being a permanent resident of the study village, in good state of health
2. Able and willing to provide informed consent
3. Age 5 years or above and weight of 20 kg or above.

Exclusion criteria

1. Signs of active leprosy
2. Signs of active pulmonary tuberculosis (cough ≥ 2 weeks duration)
3. Signs of active extra-pulmonary tuberculosis (bluish-red nodules that cover the lymph nodes, bones or joints, or cervical glands with discharge)
4. History of liver- or kidney disease
5. Allergy to rifampicin or bedaquiline
6. Having received rifampicin or bedaquiline (if applicable) in the last 2-year period
7. Not able to swallow bedaquiline 100 mg tablets
8. Self-reported (suspected) pregnancy or breastfeeding
9. Concurrent (within the last three week period before D0) use of medications not included in the safe list (for bedaquiline only)
10. QT-prolongation of ≥ 450 msec in baseline ECG within the last week.

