4.4 Randomization

For the phase 2 safety study we will first complete the final survey round of the PEOPLE study and then enumerate all those aged 5 years or above, weighing 20 kg or above and not currently suffering from leprosy. They will be divided into three age categories, 5-12 years, 13-17 years, and 18 years and above. We will then determine the overall proportions of the three age groups, the proportion multiplied by 150 will be the number of participants to be recruited per study arm for each age group. Next we will prepare sealed envelopes containing a note indicating either BE-PEP or SDR-PEP as PEP regimen, 300 in total. They will be divided into three groups with equal numbers per PEP regimen, one group of envelopes for each of the three age categories.

The next step will be to enroll the required numbers of adults (age 18 years and above) by visiting the households one by one and inviting eligible subjects to be enrolled. Each time a person agrees, an envelope will be drawn and either SDR-PEP or BE-PEP will be provided as indicated on the note inside the envelope. This process will continue until all envelopes for adults have been allocated. Provided no concerning adverse events are observed, the procedure will be repeated for the 13-17 years old. Again if no concerning adverse events are observed, the 5-12 years old will be enrolled following the same procedure. The remainder of the village population aged 2 years and above and not meeting other exclusion criteria will then be offered SDR-PEP.

Randomization for study arms 1 and 2 of the phase 3 study, will take place upon completion of the baseline survey. We will then arrange all villages by island and by group (former arm 1, 2, 3 or 4 or new villages), in order of decreasing prevalence. As was explained earlier, Fomboni, the capital of Mohéli, will be split into two clusters. Thus we will arrive at 22 pairs of clusters. Blocked randomization will be used to allocate clusters into the two study arms. The randomization schedules will be prepared by an independent sponsor biostatistician. The randomization list will be prepared using SAS 9.4 (SAS Institute, Cary NC).

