## 2. Study design and objectives

### 2.1. Study design

This is a single-site, randomized, non-inferiority, phase 2 clinical trial, comparing the safety between a single dose rifampicin (SDR-PEP) and single dose bedaquiline plus rifampicin (BE-PEP) among contacts of recent leprosy cases. Safety will be closely monitored and evaluated by an independent data and safety monitoring board (DSMB). The study setting is the village of Gégé, Anjouan, that is part of arm 1 of the PEOPLE trial in which 8 new cases have been diagnosed since 2019 but no PEP has been provided.

During the final survey round of the PEOPLE study, all individuals in the village aged 5 years or above, weighing 20 kg or above and not currently suffering from leprosy will be enumerated and screened for the study inclusion and exclusion criteria (see 5Description of analysis populations Description of analysis populations for more details).

Three hundred of the eligible individuals from the village will be stratified proportionally over three age-groups (18 years and above, 13-17 years, and 5-12 years) and will be randomized (1:1) into one of the two study arms:

- Arm 1: single dose of bedaquiline plus rifampicin (BE-PEP) (n=150)
- Arm 2: single dose of rifampicin (SDR-PEP) (n = 150)

Randomization will occur sequentially, first enrolling persons above 18 years of age. Provided no concerning adverse events are observed, the randomization and enrollment will continue for the 13-17 years old age category. Again if no concerning adverse events are observed, the enrollment will proceed for children aged 5-12 years old. The remainder of the population of this village aged 2 years and above will be offered single dose rifampicin as per WHO recommendations.

All randomized participants will be followed up closely with active monitoring for adverse events, including measurement of the corrected QT interval and liver function, before and after administration, as well as any other adverse events, including but not limited to gastro-intestinal (nausea, vomiting), nervous system-related (headache, dizziness) and cutaneous reactions.

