## 3.2. Definitions

**QT interval:** The measured QT will be corrected by the Fridericia formula through a dedicated calculator. At baseline, QTc prolongations are defined as QTc > 450ms. Participants with a QTc value above the cut-off point will be excluded from the study. Their QTc measurement will be entered in the database and will be used in the analysis to describe the baseline QTc distribution in the population.

**Liver function measurements:** ALT and AST (U/L) will be measured at baseline (day 0) and on day 14. In both time points, participants with ALT and/or AST > 3x upper limit normal (ULN) will be considered to have abnormal (elevated) values. If a participant has an elevated ALT/AST result at recruitment, they will be excluded from the study. The ULN values for ALT and AST used for this study are 55 U/L and 48 U/L respectively (<https://www.mayoclinic.org/tests-procedures/liver-function-tests/about/pac-20394595#:~:text=Normal%20blood%20test%20results%20for,8%20to%2048%20U%2FL>). Potassium and magnesium levels will only be recorded in case of QTc prolongation,  $\geq 500$  ms at baseline or  $> 60$  ms increase as compared with baseline. Analysis of this data (potassium and magnesium results) will be purely descriptive.

Adverse events' categories and how they will be summarized are further described in section 6.3.

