### **6.2. Secondary safety analysis**

#### **Baseline measurements**

Data from all screened patients with QTc, ALT or AST results will be used to determine the baseline distribution of the underlying population. Data will be described both visually and by using standard summary statistics for the whole population and by demographic characteristics, such as age (same age categories as the ones used for stratified randomization) and sex. The proportion of study participants with ALT/AST values above the normal range ( $> 3$  ULN) will be calculated together with 95% Wilson confidence intervals. The proportion of study participants with QTc values above the normal range ( $> 450$  ms) will be calculated together with 95% Wilson confidence intervals.

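### Phase 2 groups are called random samples and used to describe baseline QTc and ALT/AST in the population, but Protocol 4.4 recruits household by household until the envelopes run out

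*SAP*

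**What the plan says.** Three places in the protocol call the phase 2 groups random samples:

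- The Synopsis plans to "offer a single dose of BE-PEP to a random sample of 150 people screened aged 5 years and above".
- Section 3.1 says of those receiving rifampicin only: "Of those a random sample of 150 will also be subjected to the same procedures".
- Section 4.2 states: "A random sample of 150 eligible participants will receive BE-PEP, the remainder will receive SDR-PEP".

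Section 4.4 gives the procedure. After the final PEOPLE survey round, villagers aged 5 or above, weighing 20 kg or above and without leprosy are listed, and the 300 envelopes are divided over three age groups. Adults are then recruited "by visiting the households one by one and inviting eligible subjects to be enrolled". An envelope is drawn for each person who agrees. "This process will continue until all envelopes for adults have been allocated". The same steps are repeated for ages 13-17 and then 5-12.

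The first secondary objective (Protocol 2.1.2, SAP 2.2.2) is the baseline frequency of QTc prolongation and ALT/AST elevation in the population. SAP 6.2 says: "Data from all screened patients with QTc, ALT or AST results will be used to determine the baseline distribution of the underlying population", with Wilson intervals for the proportions. SAP 3.2 keeps the QTc of people excluded at baseline, and that measurement "will be used in the analysis to describe the baseline QTc distribution in the population". SAP 2.1 says that all villagers of eligible age and weight without current leprosy "will be enumerated and screened for the study inclusion and exclusion criteria".

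**The concern.** Drawing an envelope randomizes a person to an arm. It does not randomize who is invited. Under 4.4 a person's chance of being measured depends on where the household falls in the visiting order, on being at home and on agreeing. No random order of households or persons is specified.

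The plan nevertheless presents the result as the population's. That wording is justified if the people measured are a random sample of the village or nearly all of it. The first is promised but not implemented. The second is suggested by SAP 2.1 but is not provided for in 4.4. At stake is whether the first secondary objective can be answered for the village as worded.

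**Working it through.** **The figure the plan gives for this sample size.** Protocol 4.3 states 99% power with 150 per arm, a 10 ms margin and an SD of 20 ms. The standard error is 20 × √(2/150) = 2.31 ms, and 10/2.31 = 4.33. Power is Φ(4.33 − 1.645) = 0.996 at one-sided 5%, and Φ(4.33 − 1.96) = 0.991 at one-sided 2.5%. The figure reproduces and is not in dispute. The documents state no sampling fraction and no precision target for the baseline frequencies.

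**Who would be measured.**

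- The PEOPLE survey in Gégé is placed in May 2022 in Protocol 3.1, 4.2 and 5.1 (June in the Synopsis). Phase 2 is planned for July 2022 (3.1, 7.2.1).
- Baseline ECG and ALT/AST must fall within one week before dosing (4.2, 5.1, 5.2.1).
- Dosing is staggered by age group (4.2, 4.4).
- Table 2 places consent, ECG and bloods together in the phase 2 screening visit.
- The enumeration in 4.4 uses only age, weight and leprosy status.

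The survey therefore cannot supply the ECG and blood results for the whole village. Nothing in the plan requires them for people not approached before their age group's envelopes are used.

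**Share of the eligible village enrolled.** Inputs: population 908 (4.3) or about 900 (4.2); 300 envelopes (4.4); 27% too young or light, a phase 3 figure (4.3) borrowed here for Gégé; 83% PEP uptake in PEOPLE (4.3), also borrowed.

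- Central: 908 × (1 − 0.27) = 663; 300/663 = 45%.
- 20% to 30% too young or light: 300/(908 × 0.80) = 41% to 300/(900 × 0.70) = 48%.
- Same range if only 83% would take part: 300/(908 × 0.80 × 0.83) = 50% to 300/(900 × 0.70 × 0.83) = 57%.

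SAP 6.2 uses everyone screened with a result, so the share measured is somewhat higher. With an assumed 30 screen failures, 330/663 = 50%.

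**How selection acts on the estimate.** If a fraction f is measured with frequency p1 and the rest have frequency p2, the village value is f × p1 + (1 − f) × p2. The error is (1 − f) × (p2 − p1). At f = 41% to 57%, each percentage point of difference shifts the estimate by 0.59 to 0.43 points. With illustrative rates, which are assumptions, and f = 0.45:

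- p1 = 2%, p2 = 4%: village value 3.1%, inside the Wilson interval for 6/300 (0.9% to 4.3%).
- p1 = 2%, p2 = 8%: village value 5.3%, outside it.

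Only a large difference between those reached and not reached would mislead. The documents give no evidence of such a difference.

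**Whether the Wilson interval is too narrow.** For an illustrative 7/330 the Wilson interval is 1.0% to 4.3%. An assumed household design effect of 1.5 alone gives an effective n of 330/1.5 = 220 and 0.9% to 5.0%. If the target is the village, however, about half of it has been measured. The finite-population factor is 1 − 330/663 = 0.50, the net factor is 1.5 × 0.50 = 0.75, the effective n is about 438, and the interval is about 1.1% to 3.9%. The planned interval is not shown to be too narrow.

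**The case against.** The strongest defence is that SAP 2.1, written for phase 2, describes screening of the whole eligible village, which would make the baseline data a near-census. In addition, Protocol 12.7 places pre-recruitment at the study house, and 4.4 does not say how people were called to it. This stands in part: that the people measured are those in the households visited first is an inference from 4.4, not a statement in the plan. But the timing rules prevent the survey from supplying the ECG and blood results, so the near-census reading does not settle the matter.

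A second defence is that random sample simply means random allocation. That does not fit the Synopsis and 3.1, which sample the monitored SDR-PEP group from all those receiving rifampicin only. Under 4.4 that group is whoever drew an SDR-PEP envelope, and the rest of the village is offered SDR-PEP afterwards.

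A third is that the SAP already goes part of the way. Section 6.2 computes its proportions among study participants, 3.2 retains people excluded for QTc, and 4.1 reports numbers screened and reasons for exclusion. This stands and limits the problem. The objectives still refer to the population, and 4.1 does not name the numbers approached or refused.

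A reader might also infer more than the documents support:

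- **That whole households enter together, so the Wilson intervals are too narrow.** Age groups enter in separate waves (4.2, 4.4) and SAP 6.5.1 analyses by age group. The design effect is assumed, and the large sampling fraction offsets it.
- **That an error here carries over to phase 3 recipients, who get no ECG or liver tests.** Gégé is one purposively chosen village that is not part of phase 3. A random order within it would not make it represent the 44 clusters, and any count of affected recipients would rest on invented rates.

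**Conclusion.** The point holds as an inconsistency between the random-sample label, the population wording of the first secondary objective, SAP 2.1, and the recruitment procedure in Protocol 4.4. That procedure is consecutive household recruitment with age quotas. It would enrol roughly 41% to 57% of eligible villagers. That range rests on the borrowed assumptions of 20% to 30% too young or light and up to 17% non-participation. The direction and size of any selection effect are unknown.

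The randomized comparison of QTc between arms is unaffected. The outcome for the primary objective is DSMB advice drawing on QTc data, adverse events and stopping criteria (Protocol 2.1.1), and no threshold is attached to the baseline frequencies. The effect is limited to a descriptive secondary objective for Gégé. The change is still worth making because it costs little and gives the design the property that the protocol already claims.

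**What to change.** 1. In Protocol 4.4 and SAP 2.1, put the households, or the individuals within each age group, from the enumeration list in random order. Invite in that order until the age group's envelopes are used.
2. Reconcile SAP 2.1 with Protocol 4.4 on who receives the baseline ECG and ALT/AST.
3. If recruitment has already followed the house-to-house order, remove the random-sample wording from the Synopsis, 3.1 and 4.2. In SAP 3.2 and 6.2, describe the baseline frequencies as those among the people screened, and report the numbers approached, refused and measured.

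The Wilson intervals can stay as planned. The cost is a few lines of text, since 4.4 already requires the list. The one practical drawback is a less efficient walking order in a village of about 900 people.

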## 4. Description of study population

### 4.1. Participant accounting

The number of participants screened, those who meet the study inclusion criteria and enrolled (randomized) or excluded will be summarized according to reason for exclusion. Of the enrollees, the number of participants discontinued or lost to follow-up will be recorded by reason and time of discontinuation. Additionally, the number and proportion of participants who were excluded at baseline because of a QTc  $> 450$  ms, as well as the number of exclusions due to elevated AST or ALT will be described by treatment arm and age stratum. These figures will be summarized in a CONSORT flow diagram. A table summarizing the enrolment process by treatment arm will also be produced.

### 4.2. Description of study population

Participants in each treatment group and overall will be described with respect to selected baseline characteristics, both by age strata and by allocation arm. The description will be in terms of medians and interquartile ranges for continuous characteristics and using counts and percentages for categorical

characteristics. Differences between the two arms will be noted, but no formal statistical testing will be performed.

## 5. Description of analysis populations

### 5.1. Analysis populations

For the safety analysis, both an intention-to-treat (ITT) and a per-protocol (PP) approach will be adopted. In both ITT and PP populations, participants will be analyzed according to their administered treatment. The PP population will be the primary analysis population as indicated for non-inferiority studies by the ICH-E9 guidelines.

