9. STATISTICAL ANALYSIS

The statistical analysis will be described in the statistical analysis plan (SAP), written by the biostatistician, which is binding and will be finalized before database lock or before any other analysis takes place.

9.1 Baseline characteristics:

Both an intention to treat (ITT) and a per-protocol (PP) approach will be used to define the analysis populations in both phase 2 and phase 3 studies. In the Intention-to-Treat analysis, all participants will be analyzed according to their randomized allocation, even in case they do not receive the randomized treatment, show protocol violations prior to or during the study.

In the per-protocol analysis only participants who received PEP as planned, have completed follow-up, and follow the protocol as planned are included.

In the phase 2 study, the PP population will be the primary analysis population as indicated for non-inferiority studies by the ICH-E9 guidelines. For the phase 3 study, the intention to treat will be the primary approach.

The number of participants screened and enrolled or excluded will be summarized according to reason for exclusion. Of the enrollees, the number of patients discontinued or lost to follow-up will be recorded by reason and time of discontinuation. These figures will be summarized in a CONSORT flow diagram.

Subjects in each treatment group will be described according to baseline characteristics. The description will be in terms of medians and interquartile ranges for continuous variables and using counts and percentages for categorical variables. Standard statistical tests of significance of imbalance in baseline characteristics will be performed.

9.2. Phase 2 study:

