#### 5.1.1. *Intention to treat (ITT) analysis*

In the Intention-to-Treat analysis, all participants will be analyzed according to their administered allocation, even in case they show protocol violations prior to or during the study.

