#### 5.1.2. *Per protocol (PP) analysis*

An analysis based on a “per protocol” approach will be conducted to assess the non-inferiority of treatments, as recommended for non-inferiority studies. Thus, analyses based on the subjects following the study protocol will be the main strategy of analysis adopted for the primary and secondary endpoints. In the per-protocol analysis only participants who received PEP as planned, have completed follow-up, and follow the protocol as planned are included.

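### The phase 2 SAP gives the name ITT to a set assigned by treatment taken, contrary to protocol 9.1, so no QTc analysis in the SAP keeps switchers in their randomized arm

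*SAP*

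**What the plan says.** Protocol 9.1 sets the rule. It says that an ITT and a PP "approach will be used to define the analysis populations in both phase 2 and phase 3 studies". Under ITT, "all participants will be analyzed according to their randomized allocation, even in case they do not receive the randomized treatment". Protocol 4.5.2 is consistent with this: people withdrawn from the intervention stay in follow-up because they belong to the ITT population.

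The phase 2 SAP says something else. Section 5.1: "In both ITT and PP populations, participants will be analyzed according to their administered treatment". Section 5.1.1 repeats it for ITT: "all participants will be analyzed according to their administered allocation". That sentence otherwise follows the protocol's closely, but it leaves out the clause on not receiving the randomized treatment. Section 5.1.2 limits PP: "only participants who received PEP as planned, have completed follow-up, and follow the protocol as planned are included".

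Both documents make PP primary for phase 2; the protocol's wording is "In the phase 2 study, the PP population will be the primary analysis population as indicated for non-inferiority studies by the ICH-E9 guidelines". On the SAP's standing, protocol section 9 says: "The statistical analysis will be described in the statistical analysis plan (SAP), written by the biostatistician, which is binding".

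SAP 6.1 lists the QTc comparisons (difference in means at 24 hours, ANCOVA on baseline QTc, change scores) and names no further population. SAP 4.2 refers to the allocation arm only for describing baseline characteristics.

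**The concern.** Two current definitions of the same named analysis contradict each other, and the SAP gives no reason for departing from the protocol. Consider a participant who draws a BE-PEP envelope but takes only rifampicin. The protocol counts that person as BE-PEP in the ITT analysis. The SAP counts them as SDR-PEP in its ITT set and drops them from PP.

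In a non-inferiority comparison an analysis by randomized allocation is normally set beside PP, because only the former preserves the randomized groups. Under the SAP neither set does. A reader of the phase 2 report who saw ITT and PP agree would take the ITT result to be the analysis that the protocol describes, and it would not be. The report goes to the DSMB before the decision on phase 3.

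**Working it through.** **1. The definitions side by side.**

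| Participant | Protocol 9.1 ITT | SAP ITT | SAP PP |
|---|---|---|---|
| Allocated BE-PEP, took BE-PEP | BE-PEP | BE-PEP | BE-PEP |
| Allocated BE-PEP, took rifampicin only | BE-PEP | SDR-PEP | excluded |
| Allocated BE-PEP, took nothing | BE-PEP | no arm defined | excluded |

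No SAP column keeps the second participant as randomized. For PP the reference to administered treatment does no work, since PP holds "only participants who received PEP as planned".

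**2. Planned power.** Inputs: SD 20 ms and 150 per arm (protocol 4.3); margin +10 ms and a one-sided 95% interval (protocol 4.3, SAP 6.1); true difference 0 (protocol 4.3).
- SE = 20 × √(2/150) = 2.31 ms.
- Power = Φ(10/2.31 − 1.645) = 99.6%, against 99% stated. This reproduces. The choice of ITT rule changes neither the planned n nor the planned power.

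**3. Size under assumed switching.** The documents give no switching rate and no QTc gap, so both are assumptions. Let k of the 150 allocated BE-PEP take SDR-PEP, with none switching the other way. Let switchers' underlying QTc be b ms longer than that of the rest, with k people of the same type in the SDR-PEP arm. The true difference is 10 ms, so a declaration of non-inferiority is an error with nominal rate 5%.

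- Randomized ITT: expected difference 10 × (1 − k/150), so the shift towards zero is 10k/150. This is dilution and does not depend on b.
- As-treated, unadjusted: BE-PEP has 150 − k people, none of the long-QTc type; SDR-PEP has 150 + k, of whom 2k are. Shift = 2kb/(150 + k).
- PP, unadjusted: 150 − k against 150. Shift = kb/150.
- Error = Φ(shift/SE − 1.645), with SE = 20 × √(1/n1 + 1/n2) for the group sizes concerned.

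| k | Randomized ITT (any b) | As-treated, b = 0 | As-treated, b = 10 | As-treated, b = 20 | PP, b = 20 |
|---|---|---|---|---|---|
| 0 | 5.0% | 5.0% | 5.0% | 5.0% | 5.0% |
| 3 | 6.0% | 5.0% | 7.0% | 9.6% | 7.0% |
| 5 | 6.7% | 5.0% | 8.6% | 13.9% | 8.7% |
| 8 | 7.9% | 5.0% | 11.4% | 22.1% | 11.7% |

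Example, k = 8 and b = 20: shift = 2 × 8 × 20/158 = 2.03 ms, giving 22.1%. Randomized ITT at k = 8: shift = 10 × 8/150 = 0.53 ms, giving 7.9%.

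**4. Effect of baseline adjustment.** If the gap b is fully present at the baseline ECG, change scores subtract it and the as-treated shift becomes zero. ANCOVA with baseline slope β leaves (1 − β) of the shift. Any part of the gap that is not present at baseline remains. The as-treated columns for b = 10 and 20 therefore apply only to the unadjusted comparison.

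**The case against.** The strongest case against is that this changes little.

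- PP is primary in both documents and excludes switchers whichever ITT wording applies. This stands: the conflict reaches only the supporting analysis.
- Analysis by treatment received is usual for safety data, and SAP 5.1 introduces these sets for the safety analysis. This stands for adverse events and liver results. It does not justify calling the set ITT when the protocol defines that term otherwise.
- Randomized ITT has its own weakness, because it dilutes a true QTc difference. This stands. With b = 0 it is the worse of the two.
- SAP 6.1 already includes baseline-adjusted analyses. This stands to the extent that the gap exists at baseline.
- Switching may be rare. A single dose is taken under observation after the envelope is drawn, and QTc of 450 ms or more, medicines off the safe list and inability to swallow the tablets are exclusions. This is fair, but it is not certain: concomitant medication is recorded again at D0, and the safe-list exclusion applies to bedaquiline only.
- A person who took nothing has no QTc 24 hours after dosing, so an ITT set requiring a 24-hour ECG may not recover them. This stands.
- The SAP cites protocol version 2.1, and the protocol at hand may be later. That could explain the mismatch but does not remove it.

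A reader might go further and infer that the SAP tilts the phase 2 decision towards declaring BE-PEP safe. The documents do not support this. The deciding population is unchanged, protocol section 8 leaves the clinical relevance of any QTc prolongation to the DSMB, and nothing in the documents shows that people who do not take bedaquiline have a longer QTc.

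**Conclusion.** The contradiction is real and stands in current text: the SAP's ITT set is an as-treated set, and no QTc analysis in the SAP keeps switchers as randomized. This is true of the SAP only; the protocol still promises the randomized analysis, so the two must be reconciled. The primary PP analysis is unaffected by the conflict.

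The effect is zero without switching. If switching is unrelated to QTc, as-treated analysis is unbiased and randomized ITT dilutes. If switchers have longer QTc, the unadjusted as-treated comparison is biased towards non-inferiority, in the same direction as PP and by about twice as much, so agreement between those two would not be an independent check. The error rates above 5% rest entirely on the assumed k and b. They should be read beside the randomized ITT column, not against 5% alone. Neither set is uniformly the stricter test, which is the reason to report both.

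**What to change.** In SAP 5.1 and 5.1.1:

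- Restore the protocol's definition for QTc as a supporting analysis: all randomized participants with a 24-hour ECG, analysed by envelope allocation.
- Keep the as-administered set under its own name (safety or as-treated set) for adverse events, liver results and a supportive QTc analysis.
- Remove the reference to administered treatment for PP, where it has no function.
- Report both supporting QTc results beside the primary PP result, with the number of switchers by arm, and state that randomized ITT can dilute a true QTc difference.

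The cost is a wording change in the SAP and one more run of the same comparison. It needs only the envelope allocation and the dose given. Sample size, planned power and trial conduct do not change.
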